[name] and [name] have completed a Phase II RCT of guided internet self-help ruminaton training intervention versus group training versus usual care for Dutch young adults (n=251, aged 15-21) who were at high risk because of elevated worry and rumination (Topper et al., 2017). Retention was 87% at 12 month follow-up and internet guided self-help significantly reduced self-reported caseness of depression and anxiety relative to usual care (15% versus 32%). In this trial, the web-based training halved self-reported caseness of major depression and generalised anxiety disorder in at-risk young adults (15-22 years old) over 1 year (Topper et al., 2017; effect size relative to usual practice, d=0.89 for reducing worry; d=0.55 for reducing symptoms of depression). This provides proof-of-principle that an internet-delivered intervention can be beneficial for promoting resilience and reducing mental ill-health in young adults. In a further trial in the UK (ISRCTN12683436), we compared therapist-supported internet self-help versus usual practice in 235 undergraduates (18-25 years) at high risk because of elevated worry and rumination, and included an unguided self-help therapy condition to examine the feasibility of this approach (n=78, see protocol, Cook et al., 2016). This pilot suggested that an unguided self-help variant of this intervention is feasible, acceptable, and potentially efficacious for young adults. There was good adherence and acceptability for internet self-help: on average (mean) 46% of self-help modules were completed, equivalent to completion rates in therapist-supported version and consistent with wider literature; 27% of users completed all modules, 14% of users never logged on, at least on par with previous e-treatment studies.

We have pre-clinical pilot data indicating the short-term benefits of training emotional perception: training improved emotion recognition in young adults, with effects persisting over four weeks, and increased cooperative outcomes with strangers in a dyadic negotiation task and independent observer ratings of positive affect (Schlegel & Hall, in preparation).

A full risk plan can be found in the Appendix section 16.1

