(a) An *achievement-focused control value self-help component* will target appraisal biases related to maladaptive emotions linked to dimensions of power and causation (internal/external attribution of causes). This self-help builds on the control-value theory of achievement emotions (Pekrun, 2006), and includes: (i) attributional retraining (targeting perceived control), a video-based short intervention that has already proved successful with college students (Perry et al., 2014); (ii) mindset training (targeting perceived control and promoting growth mind-sets; Paunesku et al., 2015); (iii) utility value self-help (targeting perceived value of achievement), which has been shown to be effective with minority students (Hulleman & Harackiewicz, 2009). Elements focused on building perceived control and a growth mindset, have been shown to reduce and prevent depression and anxiety in young people even after a single 30-min session over 9 months (Miu & Yeager, 2015; Schleider & Weiss, 2016).

(b) A *social-focused self-help component wi*ll target the systematic negative appraisals of social situations, that is, when individuals tend to make negative appraisals of ambiguous social situations (e.g., perception of rejection, criticism, exclusion). The training will build on well-established Cognitive Bias Modification-Interpretation training approaches, which have been shown to be effective at changing biases and facilitating more adaptive emotional responses in the laboratory (Cristea et al., 2015; Hallion & Ruscio, 2011; Mathews & Mackintosh, 2000), and for which there is emergent preliminary evidence of being beneficial for reducing depression and anxiety in individuals with elevated symptoms (Cristea et al., 2015; Hallion & Ruscio, 2011). The training will involve repeated exposure to ambiguous social scenarios with participants forced to adopt adaptive non-rejecting interpretations in the context of an ecologically-relevant stressor (CBM-I). Previous interventions have used text or audio-recordings to provide scenarios, and resolution is based on completing word fragments.

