10.3.3 Secondary analyses

A number of secondary analyses will be conducted.

1. 12-month follow-up comparison

Primary and secondary outcomes will be compared at 12-month follow-up using the statistical approach outlined above.

2. Repeated measures comparison including all timepoints

Primary and secondary outcome measures will be compared at all follow-up timepoints (1, 3, 12 months) using repeated measures analyses, including all participants with data available for at least one of the three follow-up timepoints.

3. Differential adherence analysis

Differential adherence within the active treatment arms is anticipated, which could impact the outcomes. Ideally, we wish to compare participants who adhere to their intervention with those in the comparator arm who would also have adhered to the treatment had they been allocated to it. To address this issue we will undertake a complier average causal effect (CACE) model, using a 2-stage least squares instrumental variable regression model. Such models will be performed for the continuous primary and secondary outcomes at 3- and 12-month follow-up using observed data only, and will include the covariates adjusted for in the linear regression models. The CACE analyses will be considered as secondary analyses. The definition of a 'complier' will be: (i) complete at least one Challenge (some psychoeducation) and at least four Challenges completed or ten Tools used (to capture practice) OR (ii) (to capture combined usage) at least ten Challenges or Tools completed (any combination), including at least one Challenge and one Tool. (The definition of a 'complier' may be subject to further revision.)

4. Imputation of missing data

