## 6.6 Differential adherence analysis

Differential adherence within the active treatment arms is anticipated, which could impact the outcomes. Ideally, we wish to compare participants who adhere to their intervention with those in the comparator arm who would also have adhered to the treatment had they been allocated to it. To address this issue we will undertake a complier average causal effect (CACE) model, using a 2-stage least squares instrumental variable regression model. Such models will be performed for the continuous primary and secondary outcomes at 3- and 12-month follow-up using observed data only, and will include the covariates adjusted for in the linear regression models (Tables A.4–A.10). The CACE analyses will be considered as secondary analyses. The definition of a 'complier' will be: (i) complete at least one Challenge (some psychoeducation) and at least four Challenges completed or ten Tools used (to capture practice) OR (ii) (to capture combined usage) at least ten Challenges or Tools completed (any combination), including at least one Challenge and one Tool. (The definition of a 'complier' may be subject to further revision.)

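### The threshold CACE versus usual care is too large if use below the complier rule helps, and the plan neither states nor tests the contrary assumption

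*SAP*

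**What the plan says.** SAP 6.6 specifies a "complier average causal effect (CACE) model, using a 2-stage least squares instrumental variable regression model" for the continuous outcomes at 3 and 12 months. Treatment received is a yes/no flag with two routes. Route (i) is "at least one Challenge (some psychoeducation) and at least four Challenges completed or ten Tools used". Route (ii) is "at least ten Challenges or Tools completed (any combination), including at least one Challenge and one Tool". Protocol 10.3.3 carries the same rule.

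The SAP adds two qualifications: "The definition of a 'complier' may be subject to further revision", and "The CACE analyses will be considered as secondary analyses". SAP 6.9 limits the CACE data set to participants whose app use was not disrupted before the 3-month follow-up. SAP 5.6 lists the numbers of Challenges completed and of tool practices among the adherence measures, to be reported descriptively. Neither document states what is assumed about participants below the rule, explains the cut-off, or plans a CACE with a different definition of treatment received.

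Two protocol statements bear on low use. Section 8, on the achievement component of the emotional competence (EC) app, reports of its control and mindset content that such elements "have been shown to reduce and prevent depression and anxiety in young people even after a single 30-min session over 9 months". Section 2.1 reports, from a pilot of an unguided rumination programme, that "27% of users completed all modules, 14% of users never logged on".

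**The concern.** An instrumental-variable analysis with a binary flag takes the whole intention-to-treat difference and divides it by the share who meet the flag. Against usual care, that quotient is the effect in compliers only if active-arm participants who miss the flag have the outcome they would have had under control. This is the exclusion restriction.

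Here the flag is a minimum dose, not a marker of any exposure. Someone who completed three Challenges and used no Tools, or one Challenge and eight Tools, is coded as untreated. Any benefit to such people stays in the numerator, while they are left out of the denominator.

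The CACE has its own row beside the intention-to-treat row in Tables A.4–A.10 and will be read as the effect of adequate use. If light use helps, that row makes adequate use look more effective than it is, and the more light users there are relative to compliers, the larger the error.

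**Working it through.** **Plan's own figure.** The documents state no complier rate, CACE effect size or CACE power, so there is nothing to reproduce.

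**The rule.** Let C be Challenges and T Tools. The natural reading is: complier if C ≥ 1 and (C ≥ 4 or T ≥ 10), or if C + T ≥ 10 with C ≥ 1 and T ≥ 1. Route (ii) matters. Six count pairs (C, T) lie below both 4 Challenges and 10 Tools and still qualify: (1,9), (2,8), (2,9), (3,7), (3,8) and (3,9). Ten Tools with no Challenge does not qualify on this reading, but would if the 'and/or' in route (i) were grouped the other way.

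**Formula, active arm versus usual care.** Let t be the true effect in compliers, and let non-users have no effect.

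- Intention-to-treat effect = pC·t + pS·k·t
- Threshold CACE = that ÷ pC = t·(1 + k·pS/pC)

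**Inputs.**

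- Never logged in: 20% (SAP 6.9).
- t = 3.0 WEMWBS points, the minimum important difference in SAP 3.4, for illustration only.
- pC, pS and k: assumptions. pC is varied from 20% to 60%, and pS = 80% − pC, which counts every logged-in non-complier as a user of active content.

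| pC | pS | k = −0.25 | k = 0 | k = 0.25 | k = 0.5 |
|---|---|---|---|---|---|
| 60% | 20% | 2.75 (−8%) | 3.0 | 3.25 (+8%) | 3.5 (+17%) |
| 40% | 40% | 2.25 (−25%) | 3.0 | 3.75 (+25%) | 4.5 (+50%) |
| 30% | 50% | 1.75 (−42%) | 3.0 | 4.25 (+42%) | 5.5 (+83%) |
| 20% | 60% | 0.75 (−75%) | 3.0 | 5.25 (+75%) | 7.5 (+150%) |

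Example: 3.0 × (1 + 0.25 × 0.50/0.30) = 4.25. A simulation of 4,000,000 participants with pC = 30% and pS = 50% gave 3.01, 4.27 and 5.49 for k = 0, 0.25 and 0.5, against 3.0, 4.25 and 5.5 from the formula.

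If some logged-in participants only self-monitor, pS falls. With pC = 40%, pS = 20% and k = 0.25 the factor is 1 + 0.25 × 0.20/0.40 = 1.125, instead of 1.25 with pS = 40%.

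**Any-use definition.** If treatment received means at least one Challenge or one Tool, the estimate is (pC·t + pS·k·t)/(pC + pS). With pC = 30%, pS = 50% and k = 0.25 this is (0.90 + 0.375)/0.80 = 1.59. It is the average effect over everyone who used any active content. If k lies between 0 and 1, the complier effect (3.0 here) lies between the any-use estimate (1.59) and the threshold estimate (4.25).

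**EC versus CBT.** The SAP does not say how treatment received is coded in this contrast. If only EC compliance is instrumented, with the same shares, k = 0.25 and an assumed CBT intention-to-treat effect of 0.5, the estimate is (0.90 + 0.375 − 0.50)/0.30 = 2.58. That is below 3.0, so the direction of error is not fixed.

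**The case against.** The strongest reply is that the bias is conditional and its size unknown. It vanishes if use below the rule does nothing and reverses if such use harms. That stands. A reader might infer that the CACE is bound to overstate; the documents do not show this.

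The low-dose evidence is also narrow. The 30-minute claim concerns part of one of four EC modules, each EC participant receives two modules, and the content is not described as part of the CBT app. The documents do not say how long a Challenge takes, so one such session might already meet the rule. The claim is a reason to examine the assumption, but does not show that light use of either app works.

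It is tempting to take the shares from the pilot: 27% finished, 14% never logged on, so 59% lay between. The pilot does suggest that partial use is common. With mean completion at 46%, and taking non-loggers as zero, the middle group averaged (46 − 27)/59, or about 32% of modules. But it was a different programme, in 78 undergraduates, and finishing every module is far stricter than the complier rule here. Those figures do not bracket pC or pS.

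Finally, the analysis is secondary, protocol 10.6 has the intention-to-treat results interpreted first, and Table A.2 will describe adherence. This limits the consequence. It does not supply the missing assumption, and a descriptive table does not correct the estimate.

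**Conclusion.** The point holds in conditional form. For each active arm against usual care, the threshold CACE equals the complier effect only if use below the rule has no effect. If such use helps in the same direction, the estimate is inflated by 1 + k·pS/pC: about 8% to 150% for pC from 20% to 60%, pS = 80% − pC and k from 0.25 to 0.5. Those shares and effects are assumptions. The range is not a forecast.

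The any-use definition is better identified. Self-monitoring is included in all three arms (SAP 3.1; protocol section 8), so an active-arm participant who opens no Challenge and no Tool receives nearly what a control participant receives.

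Two stronger conclusions do not follow. The threshold estimate cannot be labelled an upper bound throughout Tables A.4–A.10: that requires k ≥ 0, and it fails as a general label for EC versus CBT. Nor should the any-use estimate replace the threshold estimate as the basis for every statement about using the app. SAP 6.6 asks about those who adhere, which is a different question. The primary analyses are not affected.

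**What to change.** In SAP 6.6:

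1. State the assumption that active-arm participants below the complier rule have no effect relative to usual care.
2. Fix the complier rule, with the 'and/or' grouping made explicit, before allocations are revealed. SAP 7.1 places only the blinded intention-to-treat analyses before that point, and SAP 6.6 leaves the rule open without a date. SAP 1.7 treats revisions made after scrutiny of the data and unblinded interpretation as post hoc, but sets no deadline for this rule. For a given intention-to-treat effect, a stricter rule lowers pC and so raises the estimate.
3. Add a sensitivity CACE for each active arm versus usual care, with the same two-stage model and covariates and the same undisrupted participants, defining treatment received as at least one Challenge or one Tool.
4. Report it beside the threshold CACE in Tables A.4–A.10, noting that the threshold estimate may be too large versus usual care if use below the rule helps.

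The cost is a few sentences and one further run of a planned model on counts already collected. The downside is that the any-use estimate averages over light users and will be smaller in magnitude: both estimates divide the same intention-to-treat difference, and its divisor is larger.

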#### 6.7 Addressing influence of COVID-19

This trial was designed prior to the onset of the COVID-19 pandemic; hence, no account had been taken in the data collection of data analysis to address the potential effects of COVID-19, and the various restrictions and lockdowns that have been applied in all four countries that are participating in the trial, at various times during the period of participant recruitment and follow-up. To address potential effects of COVID-19 and lockdown, data will be collected to indicate whether the participant was being affected by lockdown/restrictions at the time. This data will be used in sensitivity analyses as an additional predictor (in addition to baseline scores and minimisation characteristics) for all primary and secondary outcomes.

#### 6.8 Addressing protocol violations during the recruitment procedure

As participants were being recruited via the website, it was noted that some people who were interested in joining the trial were being found ineligible, and therefore unable to participate; in some cases, the potential participant was repeating the application process using the same email address but entering different data in order to ensure eligibility. This process is designated as a

protocol violation. Such participants are allowed to join the trial, but in the light of the fact that these participants may in fact be ineligible, we will monitor the numbers of such participants, and will consider a sensitivity analysis excluding these participants, depending on the numbers.

### 6.9 Addressing protocol violations due to app outage

Due to a fire at the Monsenso site on 10/03/2021, the app was unavailable between 10/03/2021 and 25/03/2021. Therefore, participants who registered for the trial and were randomised to receiving a version of the app did not have the app available for a period of time. It is the intention that the app intervention is available to participants for the full 12-month period of follow-up. However, it is anticipated that the majority of therapeutic effect will take place during the first 4 weeks of the intervention period.

Based on a total of 2141 participants who had registered prior to the app outage:

- Those participants due both 1m and 3m FU (i.e., either completed or past the timepoint to complete) before 10 March (i.e., only 12m FU potentially impacted by lack of app availability), N = 446
- 2. Post 1m but prior to 3m FU before 10 March (i.e., potential impact of app outage on 3m and 12m FU). Those who had not reached the date their 3-month follow-up was due by 9th March but had passed the date on which their 1 month follow up was due (1 month follow up was due on or before 9th February 2021) N= 465
- 3. Those signed up to study but not completed 1m FU before 10 March (this will roughly correspond with those who signed up between 12 Feb and 10 March the participants most severely affected by the app outage potentially impact of outage on 1m, 3m and 12m FU), N = 992. This group can be further divided:
  - Never logged on: N= 319 (all have been re-invited twice) on average before the app outage, 20% of participants never signed into the app
  - Has old MSS account, N= 83 (old account not lost, badge data will be re-added)
  - Had old MSS account and account lost-AND have not set up themselves up on a new account, N= 389
  - Data lost, new account set up and ppt starting again (what badge data we have will be added back) N=201
- 4. Signed up after 25 March unaffected by app outage as there was a new server up and running when they signed up. N=238. These ppts are affected by the intermittent app stability issues, but not the fire or badge data not showing correctly

Several analytical approaches to address this issue are available.

All approaches are based on replenishment of the sample: we will recruit an additional number of participants to replace those affected by the outage. A minimum of 992 (Group 3 above) and a maximum of 1457 (Groups 2 and 3) additional participants should be recruited. Groups 1 and 4 do not need to be replaced. The overall rate of non-logins is 20%; hence it is assumed that 20% of participants recruited for replenishment would also be non-logins.

Therefore, the overall revised target recruitment is 2142 (initial sample size) plus an additional 1457 participants to replenish those disrupted by the app outage: 3599 participants in total.

Assuming adequate replenishment of the sample, a series of post hoc sensitivity analyses will be performed on the primary outcomes (WEMWBS for PROMOTE; PHQ-9 for PREVENT).

#### 3-month analyses (observed outcome data only)

The primary analysis using the intention to treat principle (all recruited participants will be analysed according to their randomised group) will be carried out using all observed data, combining data from the original sample with data from the additional participants recruited to replenish the sample following the disruption due to app outage.

For comparison with the primary analysis, two further post hoc sensitivity analyses are proposed.

- 1. Exclusion of participants whose intervention was disrupted prior to 3-month follow-up (Groups 2 and 3).
- 2. Primary analysis with addition of a covariate to indicate postulated level of disruption due to app outage (0 for Groups 1 and 4 (little/no disruption); 1 for Group 2 (moderate disruption); 2 for Group 3 (severe disruption)). Although this is a post-randomisation covariate, it is thought to be distributed randomly across treatment groups (i.e. all treatment groups were affected equally by the app outage). As an extension to this model, an interaction term, to model the interaction between treatment group and level of disruption, will be added to this model, with the aim of exploring whether there is any evidence to indicate any variation in the effect of disruption across the three treatment groups.

Comparison of these analyses will allow estimation of the between treatment group differences at specified levels of disruption (i.e. due to disruption occurring at different times during treatment delivery and follow-up). All of the above are post hoc exploratory analyses only, performed in response to the unforeseen app outage. Analysis 2 in particular, should be viewed with caution as it includes a post-randomisation covariate. However, disruption due to app outage is distributed evenly across treatment groups, and it is reasonable to assume that distribution is also effectively random (i.e. timing of recruitment is thought to be random; there is no difference between participants recruited at such a time as to be affected by the app outage and those that were not).

## 12-month analyses

Following the analysis of the 3-month outcome data, a decision will be taken on whether to include a similar set of sensitivity analyses as were undertaken using the 3-month follow-up data. Whilst it is recognised that there are issues with regard to planning subsequent analyses after viewing the results of analyses of data from a preceding timepoint, in this circumstance, it is helpful to use 3month data to inform sensitivity analyses at 12 months. If the 3-month analyses indicate little difference comparing analyses including all participants with those including non-disrupted participants only, then it is likely that sensitivity analyses at 12 months would produce similar results, as it is likely that the disruption due to app outage would have a stronger influence on treatment effect at 3 months than at 12 months.

Options for sensitivity analyses at 12-month follow-up are similar to those for 3-month follow-up. The primary analysis will again be based on the intention to treat principle: all recruited participants will be analysed according to their randomised group. This is the originally intended primary analysis and adds the participants recruited to replenish the sample following the disruption due to app outage to the original intended sample.

For comparison with the primary analysis, three further post hoc sensitivity analyses would be proposed.

- Exclusion of participants whose intervention was disrupted prior to 12-month follow-up (Groups 1, 2 and 3).
- 2. Exclusion of participants whose intervention was disrupted prior to 3-month follow-up (Groups 2 and 3; moderate/severe disruption).
- 3. Primary analysis with addition of a covariate to indicate level of disruption at the specified timepoint (0 for Groups 1 and 4; 1 for Group 2; 2 for Group 3). As an extension to this model, an interaction term, to model the interaction between treatment group and level of disruption, will be added to this model, with the aim of exploring whether there is any evidence to indicate any variation in the effect of disruption across the three treatment groups.

Comparison of these analyses with the primary analysis of 12-month data will allow exploration of the effects of disruption due to the app outage, including the effects of app outage on participants who experienced disruption at different times during treatment delivery and follow-up.

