#### Repeated measures analyses (including observed outcome data only at 1, 3 and 12 months)

Similarly to the analyses of 12-month data, we will await results of the sensitivity analyses at 3month follow-up prior to making any decisions regarding sensitivity analyses of the repeated measures analyses including data from 1-, 3- and 12-month follow-up.

Again, the primary analysis will use the intention to treat principle : all recruited participants will be analysed according to their randomised group. This is the originally intended primary analysis and adds the participants recruited to replenish the sample following the disruption due to app outage to the original intended sample.

Options for sensitivity analyses for repeated measures analyses include the following.

1. Exclusion of participants whose intervention was disrupted prior to 12-month follow-up (Groups 1, 2 and 3).

2. Exclusion of participants whose intervention was disrupted prior to 3-month follow-up (Groups 2 and 3; moderate/severe disruption).

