#### 7. General analysis considerations

#### 7.1 Timing of analyses

The first set of statistical analyses will be performed when the 3-month outcome data is available and the database has been locked. At this point, the statistician will perform the 3-month inferential analyses (as well as descriptive analyses for 1- and 3-month data), whilst being unaware of treatment arm allocation. These analyses will be performed on the ITT population using observed data only. Following presentation of the results with anonymised allocations, the allocations will be revealed for interpretation of the results. Following revelation of treatment allocations, the remaining analyses of 3-month outcome data will be performed. Following completion of 12-month data collection and database lock, the remaining analyses of the 12-month outcome data will be performed. At this point the repeated measures analyses and analyses including imputed and observed data will be performed.

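### Whether the listed 12-month and repeated-measures app-outage sensitivity analyses are run is left until the 3-month results are seen, guided only by an undefined notion of little difference

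*SAP*

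**What the plan says.** SAP 6.9 divides participants by when the March 2021 outage reached them. Group 1 (446) was past both the 1- and 3-month due dates, so "only 12m FU potentially impacted by lack of app availability". Groups 2 (465) and 3 (992) were disrupted before 3 months. Group 4 (238) signed up afterwards and is called unaffected.

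At 3 months, two sensitivity analyses are set out without condition. One excludes Groups 2 and 3. The other adds a disruption score: "0 for Groups 1 and 4 (little/no disruption); 1 for Group 2 (moderate disruption); 2 for Group 3 (severe disruption").

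At 12 months, three analyses are described, but "a decision will be taken on whether to include a similar set of sensitivity analyses as were undertaken using the 3-month follow-up data". The reasoning offered begins "If the 3-month analyses indicate little difference comparing analyses including all participants with those including non-disrupted participants only" and concludes that the 12-month analyses would then probably agree as well. For repeated measures, "we will await results of the sensitivity analyses at 3month follow-up prior to making any decisions", and two exclusions are listed as options.

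The three 12-month analyses are:
- Option 1: "Exclusion of participants whose intervention was disrupted prior to 12-month follow-up (Groups 1, 2 and 3").
- Option 2: exclusion of Groups 2 and 3 only.
- Option 3: the primary analysis plus a "covariate to indicate level of disruption at the specified timepoint (0 for Groups 1 and 4; 1 for Group 2; 2 for Group 3"), with a treatment-by-disruption interaction as an extension.

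On timing, SAP 7.1 has the 3-month inferential analyses done masked. It then says: "Following presentation of the results with anonymised allocations, the allocations will be revealed for interpretation of the results". The remaining 3-month analyses follow. Protocol 10.6 has the same order.

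**The concern.** An analysis that is run or dropped after a related result has been seen is open to selective reporting, whatever the intentions of the team. SAP 6.9 acknowledges this timing problem but adds no safeguard. Each trial has three contrasts, and there are two trials. The plan does not say which of these six comparisons counts, how close is close enough, or who decides. SAP 1.7 asks for strong justification of revisions made after unblinded interpretation, but choosing among options already listed need not be a revision.

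The 3-month comparison is also a weak basis for the choice. Group 1 sits in the non-disrupted set at 3 months, so that comparison cannot show whether losing the app later mattered to them. If the 12-month set is then skipped, nothing examines it.

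A smaller matter is that the 12-month options treat Group 1 in two ways: as disrupted in option 1, and pooled with unaffected Group 4 in option 3.

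**Working it through.** **Plan's own counts.** 446 + 465 + 992 + 238 = 2141. Groups 2 and 3: 465 + 992 = 1457. Target: 2142 + 1457 = 3599. These reproduce.

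**Sets being compared at the 3599 target.** Counting replenishment recruits as unaffected:
- All participants: 3599.
- Without Groups 2 and 3 (the 3-month exclusion and 12-month option 2): 3599 − 1457 = 2142.
- Without Groups 1 to 3 (12-month option 1): 3599 − 1903 = 1696.
- Group 1 as a share of those coded 0: 446/2142 = 21%.

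**Chance gap at 3 months with no outage effect.** Inputs are the 70:30 cohort split and 1:1:1 allocation, 60% retention (40% attrition in Protocol 10.1), and WEMWBS SD 6.0 to 11.3 (Protocol 10.1.1).

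PROMOTE participants per arm with data:
- Full: 3599 × 0.7/3 × 0.6 = 503.9.
- Subset: 2142 × 0.7/3 × 0.6 = 299.9.

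The variance of a two-arm contrast is 2 × SD²/n. Because the subset is nested in the full set, Var(difference) = Var(subset) − Var(full).

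| SD | Var full | Var subset | SD of difference | 95% limit (×1.96) |
|---|---|---|---|---|
| 11.3 | 0.507 | 0.852 | √0.345 = 0.587 | 1.15 |
| 6.0 | 0.143 | 0.240 | √0.097 = 0.312 | 0.61 |

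Against the 3.0-point MCID, 1.15 is 38% and 0.61 is 20%. At SD 11.3 the limit is 1.07 with 70% retention and 1.26 with 50%. A simulation of 200,000 repeats at SD 11.3 and 60% retention also gave 1.15.

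For PREVENT, the numbers per arm are 215.9 and 128.5. With SD 5.4, the SD of the difference is 0.429 and the 95% limit is 0.84 PHQ-9 points.

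**Masked effect.** This is the direction that matters, because it would lead to skipping the analyses. With equal retention, Groups 2 and 3 make up 1457/3599 = 0.405 of the full set. If the outage reduced a contrast by δ in those groups, the expected gap between the two estimates is only 0.405δ.
- An effect of 3.0 points wholly lost in Groups 2 and 3 gives 0.405 × 3.0 = 1.21 points, close to the 1.15 chance limit at SD 11.3.
- An effect of 3.0 points half lost gives 0.405 × 1.5 = 0.61 points, at the chance limit for SD 6.0 and well inside it for SD 11.3.

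**Group 1 coding.** Options 1 and 2 differ by 2142 − 1696 = 446, which is exactly Group 1, so comparing them isolates that group. Option 3 keeps the 3-month coding, under which Group 1 had no disruption before the endpoint. At 12 months the same people did have it, and the score has no level for them.

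**The case against.** Several points on the other side are fair.
- The wording about little difference is a rationale for why 3-month data are informative, not a formal trigger. A reader might infer a decision rule that has been left half-specified; the text does not go that far. That still leaves the decision without any rule.
- Chance gaps with no outage effect would mostly prompt extra analyses, which suppress nothing. This is right, and the chance limit alone does not show harm. The masked-effect arithmetic bears on the harmful direction.
- The upper figure uses an SD that the protocol calls conservative, and the SAP models adjust for baseline score. Adjustment would narrow the limits, but the documents give no correlation from which to say by how much.
- Coding Group 1 as 0 fits the 3-month label. SAP 6.9 also expects most therapeutic benefit in the first 4 weeks, which Group 1 had completed. A reader might see options 1 and 2 as contradictory, but they are a deliberate contrast between any disruption and moderate or severe disruption. What remains is option 3, mainly its interaction extension.
- A reader might infer that the decision will certainly be made unblinded. The 12-month text does not say so. The staged sequence in SAP 7.1 makes it likely. Under the single final lock that SAP 3.7 anticipates, the 12-month data would already be held instead.

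**Conclusion.** The point stands in limited form. The 12-month and repeated-measures outage sensitivity analyses depend on results already seen, probably with allocations known, and without a stated criterion. The comparison that guides the choice says nothing direct about the 446 people in Group 1. Its 95% chance limit for a PROMOTE contrast is about 0.6 to 1.15 WEMWBS points. This rests on full recruitment to 3599, 60% retention, SD 6.0 to 11.3, a 70:30 split, replenishment recruits counted as unaffected and no baseline adjustment. Either a chance gap or a masked real effect could decide the matter.

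It would be wrong to infer that the trial's main results are at risk. The primary ITT analyses are fixed, the 3-month outage analyses are already set out, and the analyses in question are openly post hoc and involve a secondary timepoint. Because they are listed by group and model, an omission would be visible to a reader of the SAP. The Group 1 coding is a minor clarification affecting one exploratory model.

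**What to change.** In SAP 6.9, commit now to all the listed 12-month and repeated-measures outage sensitivity analyses whatever the 3-month results show, still labelled post hoc and exploratory. This costs a few extra models on data already held and some rewording. Data collection and the primary analyses do not change.

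Minor: in 12-month option 3, give Group 1 its own level, or replace the score with a categorical group variable.

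Tidying only:
- Reconcile Group 2's date bracket with its heading. The bracket requires the 1-month follow-up to be due by 9 February, whereas the heading takes anyone past it before 10 March. People due between 10 February and 9 March meet one and not the other.
- Reconcile the outage length in SAP 6.9 (10 to 25 March) with Protocol 10.01.5 (a month).
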